3.4 TRIAL TREATMENTS

AMA1-C1/Alhydrogel[®] vaccine will be supplied to the study-site pharmacist by the Pharmaceutical Development Section, Pharmacy Department, Clinical Center, National Institutes of Health, where the vaccine was formulated and vialled. Temperatures during vaccine transport will remain between 0.5°C and 9°C. The site pharmacist will label the kit with the assigned Volunteer ID number and randomization code. The vaccine should be stored in the refrigerator at 2°C to 8°C and should not be frozen. Single-dose vials should be stored in the upright position. CPG 7909 will be supplied to the study-site pharmacist by the Malaria

Vaccine Development Branch, who obtained the adjuvant through a clinical trials agreement with Coley Pharmaceutical Group, Inc.

3.4.1 AMA1-C1/Alhydrogel[®]

3.4.1.1 Formulation and Dosage

AMA1-C1/Alhydrogel[®] malaria vaccine is supplied as a cloudy suspension in single dose vials. Each 2.0 mL vial contains 0.7 mL, of which 0.5 mL is the intended volume to be injected. 0.5 mL of vaccine contains up to the equivalent of 377 µg of aluminum as Alhydrogel[®] (800 µg of aluminum hydroxide gel per dose) onto which either 20 µg, or 80 µg of recombinant AMA1-C1 has been bound. The product conforms to established requirements for sterility, safety, and identity

3.4.1.2 Packaging and Labeling

AMA1-C1/Alhydrogel[®] malaria vaccine will be packaged in unit dose vials labeled for investigational use only.

3.4.1.3 Supply, Storage, Handling and Disposal

AMA1-C1/Alhydrogel[®] vaccine should be maintained at 2°C to 8°C until just prior to administration. Vaccine should NOT be frozen at any time.

After administration of a vaccine dose, the single-dose vial will be returned to the Pharmacy at the test site, and vials will be accounted for and stored until monitoring by the IND sponsor. The vials may then be disposed of according to site protocol. At the conclusion of vaccine administration, all unused vaccine supplies will be returned to the MVDB.

3.4.1.4 Administration

AMA1-C1/Alhydrogel[®] malaria vaccine is administered in the deltoid muscle by IM injection.

3.4.2 CPG 7909

3.4.2.1 Formulation and Dosage

The trial site pharmacy will prepare the point of injection formulation as follows. CPG 7909 is supplied as a 1.0 mL solution in 2.0 mL multi-dose vials containing 10 mg/mL without preservative. A volume of 0.08 mL of CPG 7909 (10 mg/mL) will be withdrawn from the multi-dose vial of CPG 7909 using a 300 µL insulin syringe. The 0.08 mL of CPG 7909 will be added to a vial containing 0.7 mL of AMA1-C1/Alhydrogel[®]. This point of injection formulation should yield a final injection volume of 0.55 mL to be withdrawn for each vaccination. The actual dose of injected CPG 7909 will therefore be 0.56 mg. The mixture must be administered not more than 6 hours after mixing the CPG 7909 with the AMA1-C1/Alhydrogel[®].

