1.5 DOSAGE AND ROUTE OF ADMINISTRATION

Subjects in this study will be randomized to receive either

Group A: 20 µg AMA1-C1/Alhydrogel[®] with 377 µg Aluminum and 500 µg CPG 7909

Group B: 80 µg AMA1-C1/Alhydrogel[®] with 368 µg Aluminum and 500 µg CPG 7909

Group C: 80 µg AMA1-C1/Alhydrogel[®] with 368 µg Aluminum alone

All groups will receive three injections separated by one month between injections of the same dose level. All doses will be given by IM injection in the deltoid muscle in alternating arms.

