3.2 STUDY DESIGN

The study is a dose escalating Phase 1 clinical trial in healthy adult subjects designed to evaluate the safety, reactogenicity, and immunogenicity of the AMA1-C1 malaria vaccine formulated on Alhydrogel[®] co-administered with CPG 7909. The subjects will be randomized within group to receive one of 2 doses of AMA1-C1/Alhydrogel[®] + CPG 7909 or 80 µg of AMA1-C1/Alhydrogel[®] without CPG 7909. The subjects will be blinded to which vaccine they are receiving, AMA1-C1/Alhydrogel[®] with or without CPG 7909. This study will be staggered such that dose escalation will not occur until the lower dose group has received two vaccinations at days 0 and 28. The safety data up to and including day 35 (7 days post-vaccination #2) will be reviewed prior to dose escalation by the Safety Monitoring Committee.

After providing written informed consent, subjects will undergo eligibility screening, including medical history, physical examination, hematology testing, liver and renal function testing, HIV, Hepatitis B and C screening, rheumatoid factor, anti-dsDNA and ANA testing, and urinalysis; pregnancy testing will be performed on female subjects. For participants who are eligible, the Day 0 visit will be scheduled to receive the first dose of vaccine. Subjects will be observed for immediate reactions following each vaccination for 30 minutes. Subjects will return to the clinic on Days 3, 7 and 14 following each vaccination for clinical assessment.

Seventy-five (75) subjects will be progressively enrolled into one of 3 cohorts. The first 20 subjects (Cohort 1) will be randomized at a 3:1 ratio to receive either the 20 µg dose of AMA1-C1/Alhydrogel[®] + CPG 7909 or the 80 µg AMA1-C1/Alhydrogel[®] vaccine. After review of safety data at day 35 by the Safety Monitoring Committee (SMC) the study will proceed to Cohort 2. In Cohort 2, the next 20 subjects will be randomized 3:1 to receive either the 80 µg

dose of AMA1-C1/Alhydrogel[®] + CPG 7909 or the 80 µg AMA1-C1/Alhydrogel[®] vaccine, as outlined in the table below.

		Immunization Schedule		
Cohort	Total Volunteers	Day 0	Day 28	Day 56
1	20	A (15) or C (5)	A (15) or C (5)	A (15) or C (5)
2	20	B (15) or C (5)	B (15) or C (5)	B (15) or C (5)
3	35	B (15) or C (20)	B (15) or C (20)	B (15) or C (20)
TOTAL	75	A: 20 µg AMA1-C1/424 µg Alhydrogel [®] + 500 µg CPG 7909 B: 80 µg AMA1-C1/424 µg Alhydrogel [®] + 500 µg CPG 7909 C: 80 µg AMA1-C1/424 µg Alhydrogel [®]		

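### The arms are defined by 500 µg CPG 7909 but the preparation text states 0.56 mg injected, and the design table's 424 µg Alhydrogel matches no other adjuvant figure

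*Protocol*

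**What the plan says.** **CPG 7909.** Protocol 1.5 defines the two CPG arms as "Group A: 20 µg AMA1-C1/Alhydrogel[®] with 377 µg Aluminum and 500 µg CPG 7909" and "Group B: 80 µg AMA1-C1/Alhydrogel[®] with 368 µg Aluminum and 500 µg CPG 7909". The legend of the cohort table in 3.2 repeats 500 µg for both arms, for example "20 µg AMA1-C1/424 µg Alhydrogel [®] + 500 µg CPG 7909" for Group A. Section 3.4.2.1 then sets out the pharmacy mixing: 0.08 mL of a 10 mg/mL CPG solution goes into a vial holding 0.7 mL of vaccine, and 0.55 mL is withdrawn for injection. It concludes: "The actual dose of injected CPG 7909 will therefore be 0.56 mg". Section 3.4.3 repeats the steps and the conclusion, and 5.4 confirms 0.55 mL as the injected volume.

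**Adjuvant.** Section 1.5 gives 377 µg aluminum for Group A and 368 µg for Groups B and C (for C, "Group C: 80 µg AMA1-C1/Alhydrogel[®] with 368 µg Aluminum alone"). The 3.2 table gives 424 µg Alhydrogel for all three groups, as in "80 µg AMA1-C1/424 µg Alhydrogel". Section 3.4.1.1 puts an upper limit of 377 µg on the aluminum in 0.5 mL of vaccine and adds, in the same sentence, "800 µg of aluminum hydroxide gel per dose".

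**The concern.** The sections that define the arms and the sections that tell the pharmacy what to prepare give different amounts of the component under study. Someone who reads only 1.5 or 3.2 learns that CPG recipients get 500 µg. Someone who reads only 3.4 learns that they get 0.56 mg. The adjuvant entry in the design table raises a second, separate problem: its amount agrees with no other section, and it is not clear whether it is a mass of aluminum or of gel.

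The primary objective is the safety and reactogenicity of the CPG formulation, and the effect of adding CPG at day 70 is a secondary objective. Safety and antibody results will therefore be attributed to a named CPG dose on a named adjuvant background. The Safety Monitoring Committee, the pharmacy and the authors of the final report need the same description of each arm.

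**Working it through.** **1. Reproduce the stated injected CPG dose.** Inputs from 3.4.2.1 (repeated in 3.4.3): CPG volume 0.08 mL, concentration 10 mg/mL, vaccine volume 0.7 mL, injected volume 0.55 mL.

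- CPG added: 0.08 mL × 10 mg/mL = 0.8 mg
- Total volume: 0.08 + 0.70 = 0.78 mL
- CPG injected: 0.8 mg × 0.55 / 0.78 = 0.564 mg

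The protocol's 0.56 mg is correct for its own volumes.

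**2. Compare with the arm definition.** 0.564 / 0.500 = 1.128, so 12.8% above 500 µg (12% with the rounded 0.56 mg). Section 3.2 plans 45 CPG recipients with three injections each, so the gap applies to 45 × 3 = 135 planned injections. It is systematic and not preparation scatter.

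**3. Can 500 µg be recovered?** The excess volume of a CPG injection over a plain one (0.55 − 0.50 = 0.05 mL, section 5.4) multiplied by 10 mg/mL is exactly 0.50 mg. That ignores the mixing, because part of the CPG stays in the vial with the unused vaccine. It may be where the 500 µg comes from, but the protocol does not say so.

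**4. Effect on antigen.** The 0.55 mL holds 0.7 × 0.55 / 0.78 = 0.494 mL of vaccine, or 98.7% of 0.5 mL. Antigen injected is 80 × 0.987 = 79.0 µg or 20 × 0.987 = 19.7 µg, a negligible shift.

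**5. Test the 424 µg entry on both readings.**

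| Reading of 424 µg | Compared with | Result |
|---|---|---|
| Aluminum | 377 µg (Group A in 1.5; ceiling in 3.4.1.1) | 424/377 = 1.125, 12.5% above |
| Aluminum | 368 µg (Groups B and C in 1.5) | 424/368 = 1.152, 15.2% above |
| Gel | 800 µg (3.4.1.1) | 424/800 = 0.53, 53% of it |

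Volumes do not explain it. Mixing lowers aluminum slightly (377 × 0.987 = 372 µg). The whole 0.7 mL vial would hold 377 × 0.7 / 0.5 = 528 µg. The table also gives one value to all arms where 1.5 distinguishes Group A from Groups B and C.

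**6. Test the other adjuvant figures against each other.** 377 and 368 µg belong to different groups, differ by 2.4%, and both respect the 377 µg ceiling. The 800 µg is a mass of gel, and 3.4.1.1 gives it alongside the aluminum equivalent. The documents state no conversion factor. If the gel is taken as Al(OH)₃ or AlO(OH) (an assumption), 800 µg holds about 277 or 360 µg of aluminum, which is 26.6% or 4.6% below 377. Agreement depends on the gel formula, so no contradiction can be shown from the documents.

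**The case against.** The strongest reply is that what is prepared is not in doubt. Sections 3.4.2.1 and 3.4.3 give identical volumes and 5.4 repeats the injected volume. The injected dose is disclosed twice, and the wording there suggests that the authors knew it differed from the label. The vaccine arrives already formulated and vialled, so the 424 µg entry enters no preparation step at the site. Groups A and B share the same mixing steps. The comparisons in section 9.3 (Group B with C, and A with B) and the sample size in 9.4 do not use any of these amounts.

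All of that stands, and it confines the point to how the arms are described. It does not remove it: no section calls 500 µg nominal, gives a tolerance or points to 0.56 mg, and the arm definitions are where readers look for the dose.

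A reader might also infer more than the documents support:

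- *That 0.56 mg is a miscalculation.* It is not; step 1 reproduces it. The conflict is with the 500 µg definition.
- *That the protocol gives three incompatible adjuvant amounts.* Only 424 µg is out of line. The 377 and 368 µg figures are group-specific and fit the ceiling, and 800 µg is a different quantity.
- *That the Alhydrogel amount varies about two-fold (424 against 800 µg).* This holds only if 424 µg is a gel mass. Read as aluminum, the gap is 12.5% to 15.2%.
- *That comparison with the earlier hepatitis B vaccine trial at 0.125, 0.5 and 1.0 mg CPG would be wrong.* Section 9 plans no such comparison, and 1.2.4 does not say whether those doses were nominal or injected.

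**Conclusion.** The point holds as a contradiction in the amounts that define the arms. The CPG dose is 500 µg in 1.5 and 3.2 and 0.56 mg in 3.4.2.1 and 3.4.3, a 12.8% difference on the unrounded figure, for all 45 planned CPG recipients. This rests only on the protocol's own volumes and concentration. The 424 µg Alhydrogel in the 3.2 table fits neither the aluminum figures nor the gel figure. The size of that misfit depends on its unit: 12.5% to 15.2% too high against aluminum, or 53% of the stated gel mass. No conversion factor is needed to show it.

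Power, sample size and the planned between-arm tests are untouched. What is affected is the dose to which the safety and antibody findings will be attributed. The documents do not show whether the label or the volumes carry the intended CPG dose, and nothing here should be read as choosing between them.

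**What to change.** Reconcile sections 1.5, 3.2 (table), 3.4.1.1, 3.4.2.1 and 3.4.3 with each other. The arm definitions and the preparation text should carry the same CPG 7909 amount. Each group should have one adjuvant amount on a stated basis, aluminum or gel, used throughout. The final report should state the amounts actually injected. The sponsor must determine which figures are right.

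The cost is a check with the pharmacy and the product file, then a text amendment. The analysis plan and sample size need no change.

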3.4.2.2 Packaging and Labeling

CPG 7909 will be supplied in multi-dose vials labeled for investigational use only.

3.4.2.3 Supply, Storage, Handling, and Disposal

CPG 7909 should be maintained at 2°C to 8°C until just prior to administration. CPG 7909 should NOT be frozen at any time.

3.4.2.4 Administration

After admixture with AMA1-C1/Alhydrogel[®], administration will be by IM injection in to the deltoid muscle.

3.4.3 Point of administration formulation of AMA1-C1/Alhydrogel[®] + CPG 7909

Using a 300 µL insulin syringe, 0.08 mL of CPG 7909 (10 mg/mL) will be added to a 0.7 mL vial of AMA1-C1/Alhydrogel[®] as a point of injection formulation to yield a final injection volume of 0.55 mL for each vaccination. The actual dose of injected CPG 7909 will therefore be 0.56 mg. The mixture must be administered not more than 6 hours after formulation, and should remain at 2°C to 8°C until just prior to administration.

3.5 DURATION OF SUBJECT PARTICIPATION

Subjects will be followed routinely for a maximum of 180 (± 5) days following the third vaccination. Since subjects must be screened within 56 days of vaccination, the maximum duration of subject participation in the absence of continuing adverse events is 236 (± 5) days. Subjects with adverse events will be followed to resolution or stabilization if resolution is not expected.

3.6 DISCONTINUATION OF SUBJECTS/STOPPING RULES

Circumstances under which subjects may be discontinued from the study are described in section 4.4.

3.7 ACCOUNTABILITY OF PRODUCTS

After receipt of the vaccine and/or CPG 7909, the principal investigator is responsible for distribution and has ultimate responsibility for drug accountability. A log of receipt, temperature maintenance and disposal of vaccine and CPG 7909 will be maintained by the study pharmacist.

3.8 MAINTENANCE OF STUDY CODES

Study codes will be maintained by the study pharmacist. A backup, sealed copy of the study code will be maintained by the on-site medical monitor.

3.9 DATA TO BE CONSIDERED SOURCE DATA

Study data will be entered directly onto hard copies of the eCRF, which together with paper copies of laboratory reports, will be considered the source data for the trial.

4 SUBJECTS:

4.1 INCLUSION CRITERIA

- 4.1.1 Age between 18 and 45 years, inclusive.
- 4.1.2 Good general health as a result of review of medical history and/or clinical tests.
- 4.1.3 Available for the duration of the trial (34 weeks).
- 4.1.4 Willingness to participate in the study as evidenced by signing the informed consent document.

4.2 EXCLUSION CRITERIA:

- 4.2.1 Pregnancy as determined by a positive urine β -hCG (if female) at any point during the study.
- 4.2.2 Participant unwilling to use highly effective contraception methods (such as: abstinence, birth control pills or birth control patches or vaginal ring, diaphragm with spermicide, IUD (intrauterine device), condom with spermicide, progestin implant or injection, surgical sterilization (hysterectomy, bilateral oophorectomy, tubal ligation), or a partner who has had a vasectomy) for the duration of the trial (if female).
- 4.2.3 Currently lactating and breast-feeding (if female).
- 4.2.4 Evidence of clinically significant immunosuppressive, neurologic, cardiac, pulmonary, hepatic, rheumatologic, autoimmune, or renal disease by history,

physical examination, and/or laboratory studies including urinalysis (see Appendix 17.3).

- 4.2.5 Behavioral, cognitive, or psychiatric disease that in the opinion of the investigator affects the ability of the volunteer to understand and cooperate with the study protocol.
- 4.2.6 Laboratory evidence of liver disease (aspartate aminotransferase greater than 1.25 times the upper limit of normal of the testing laboratory).
- 4.2.7 Laboratory evidence of renal disease (serum creatinine greater than the upper limit of normal of the testing laboratory).
- 4.2.8 Laboratory evidence of hematologic disease (absolute neutrophil count $<1,500/\text{mm}^3$; hemoglobin < 0.9 times the lower limit of normal of the testing laboratory, by sex; or platelet count $<140,000/\text{mm}^3$).
- 4.2.9 Other condition that in the opinion of the investigator would jeopardize the safety or rights of a volunteer participating in the trial or would render the subject unable to comply with the protocol.
- 4.2.10 Participation in another investigational vaccine or drug trial within 30 days of starting this study, or while this study is ongoing.
- 4.2.11 Volunteer has had medical, occupational, or family problems as a result of alcohol or illicit drug use during the past 12 months.
- 4.2.12 History of a severe allergic reaction or anaphylaxis.
- 4.2.13 Severe asthma (emergency room visit or hospitalization within the last 6 months).
- 4.2.14 Serologic evidence of infection with HIV-1, HBV, or HCV.
- 4.2.15 Use of corticosteroids (excluding topical or nasal) or immunosuppressive drugs within 30 days of starting this study or while the study is ongoing.
- 4.2.16 Receipt of a live vaccine within past 4 weeks or a killed vaccine within past 2 weeks prior to entry into the study.

- 4.2.17 History of a surgical splenectomy.
- 4.2.18 Receipt of blood products within the past 6 months.
- 4.2.19 Previous receipt of an investigational malaria vaccine.
- 4.2.20 Receipt of antimalarial prophylaxis during the past 12 months.
- 4.2.21 Prior malaria infection.
- 4.2.22 Travel to a malaria-endemic country during the past 12 months or planned travel to a malaria-endemic country during the course of the study.
- 4.2.23 History of a known allergy to nickel.
- 4.2.24 Pre-existing autoimmune or antibody mediated diseases including but not limited to: systemic lupus erythematosus, rheumatoid arthritis, multiple sclerosis, Sjogren's syndrome, autoimmune thrombocytopenia; or laboratory evidence of possible autoimmune disease determined by a positive anti-dsDNA titer, positive rheumatoid factor, proteinuria and/or a positive ANA.
- 4.2.25 Chloroquine and related compounds within 12 weeks of study entry.

4.3 ASSIGNMENT TO GROUPS

The three stages will be enrolled consecutively, with movement from one stage to the next dependent on assessment of day 35 safety data from the previous stage. In stage 1, subjects will be randomized to receive either 20 µg of AMA1-C1/Alhydrogel® with CPG 7909 or 80 µg of AMA1-C1/Alhydrogel® alone, and in stage 2, subjects will be randomized to receive 80 µg AMA1-C1/Alhydrogel® with or without CPG 7909. In stage 3, additional subjects will be randomized to 80 µg AMA1-C1/Alhydrogel® with or without CPG 7909.

4.4 SUBJECT WITHDRAWAL/DISCONTINUATION

Individual subjects will not receive further doses of vaccine if they meet any of the following criteria:

- 4.4.1 Treatments that could potentially interfere with vaccine-induced immunity:

The following criteria should be checked at each visit. If any become applicable during the study, the participant will be excluded from receiving further doses of the study vaccine and will not be included in the immunogenicity evaluations. The participant will, however, be encouraged to remain in the safety evaluation for doses already received.

1. Use of any investigational drug or vaccine other than the study vaccine during the study period.
2. Administration of chronic (defined as more than 14 days) immunosuppressants or other immune-modifying drugs within six months of vaccination. (Topical steroids are allowed.)
3. Administration of immunoglobulins and/or any blood products up to 30 days after the last dose of vaccine.

4.4.2 Development of Contraindications to vaccination:

The following criteria should be checked prior to each immunization and are contraindications to further immunization. However, the participant will be encouraged to remain in the safety evaluation for doses already received.

1. Hypersensitivity reaction following administration of the study vaccine.
2. Positive urine β -hCG.
3. Development of a serious or severe, vaccine-associated adverse event.
4. Development of proteinuria or positive antibody to dsDNA in the setting of a newly positive ANA.

4.4.3 Indications for deferral of vaccination:

The following events constitute grounds for deferral of vaccine administration at that point in time; if any one of these adverse events occurs at the time scheduled for vaccination, the participant may be vaccinated at a later date, within the allowable time interval specified in the protocol, or withdrawn at the discretion of the investigator. The participant must be followed until resolution of the event as with any adverse event. If the participant is withdrawn from the study, he/she will be encouraged to remain in the safety evaluation for the duration of the study.

1. Oral temperature > 37.5 °C at the time of vaccination will warrant deferral of immunization until fever and symptoms resolve.
2. Any other condition that in the opinion of the investigator poses a threat to the individual if immunized or that may complicate interpretation of the safety of the vaccine following immunization.

Such individual(s) will be followed until the symptoms resolve or the window for immunization expires. No further vaccination will be performed if the participant does not recover (oral temperature $\leq 37.5^{\circ}\text{C}$ and/or lack of symptoms) within 7 days of the originally scheduled vaccination date. The participant, however, will be followed for safety and immunogenicity. If the individual meets any of the above criteria for deferral on the day of first immunization the investigator may elect to exclude the participant from further participation in the study.

If a subject withdraws or is withdrawn prior to completion of the study, the reason for this decision must be recorded in the case report forms. If a subject is withdrawn because of an AE or SAE, the subject must be followed until resolution or stabilization of the event.

5 TREATMENT OF SUBJECTS

5.1 SCREENING (UP TO 56 DAYS PRIOR TO VACCINATION)

1. Explain the study and Informed Consent form to the volunteer.
2. Ensure the subject has signed the Informed Consent form and HIV testing informed consent form and receives a signed copy of both consent forms.
3. Elicit a complete medical history, including menstrual and contraceptive history and/or history of surgical sterility for female subjects.
4. Administer a complete physical examination.
5. Obtain blood for hematology, biochemistry, anti-dsDNA, ANA, rheumatoid factor, and serologic tests for viral hepatitis and HIV in all subjects.
6. Obtain urine for urine dipstick testing, as well as β -HCG testing in females.
7. Counsel females to avoid becoming pregnant during the study.

5.2 ENROLLMENT:

Subjects who meet all entry criteria will be invited to return to the study site to enroll in the study. At that time, all procedures will be reviewed with the subject, and if agreeable, the subject will be randomized and vaccinated.

